Transition zone biopsies will be performed at Visit 2, 30 days before treatment, and again at 3 months post-treatment. A total of 6 biopsy cores (i.e. 3 cores from the left and right transition zone) will be obtained from each volunteer. Prostate biopsy cores will be rapidly snap frozen in liquid nitrogen in coded and labeled containers and sent to [name] laboratory located at University of Texas Health Science Center - Houston Medical School for further processing.

A Randomization

Volunteers will be randomized using a blocked randomization approach by the MEDVAMC Research Pharmacy to either: ARM 1: onaBoNT-A 200 U prostate injection and placebo oral capsule daily or ARM 2: Placebo prostate injection (saline) and tamsulosin 0.4 mg capsule daily. Subjects will be randomized into one of the two treatment arms, using a block size of 4. The order in which the treatments are assigned in each block is randomized and this process is repeated for consecutive blocks of subjects until all subjects are randomized. This process ensures that after every fourth randomized subject, the number of subjects in each treatment group is equal. The MEDVAMC will prepare both pills (i.e. tamsulosin and placebo pill) and injections (i.e. onaBoNT-A and placebo saline injection) so that the study subject, investigator and all personnel treating or evaluating the subject will be blinded to treatment allocation.

B Schedule Of Events During Treatment Protocol

Tests/Time	Visit 1: Screening	Visit 2: Biopsy	Visit 3: Injection (4 weeks Post- biopsy ± 3 days)	Visit 4: Telephone Visit (Day 3 Post Prostate Injection)	Visit 5: Telephone Visit (1 Week Post- Injection ± 3 days)	Visit 6: (4 Weeks Post- Injection ± 3 days)	Visit 7: End of Study (3 months Post Injection ± 3 days)
Physical with DRE	X						X
Medical History	X						
Vital signs	X	X	X			X	X
Flowrate	X					X	X
PVR	X					X	X
PSA	X						X
CBC /platelet count	X						
Urinalysis (dipstick)	X	X	X			X	X
Biopsy(Transrectal Ultrasound Guided - TRUS)		X					X
Prostate Volume		X					X
Antibiotic		X	X				X
Fleets Enema		X	X				
Anesthesia (periprostate block)		X	X				
onabotulinumtoxin A or saline injection via TRUS			X				
Informed Consent	X						
Antibiotic dispensing	X	X				X	
Instructions to stop alpha blocker meds 7 days prior to biopsy	X						
Drug/Placebo dispensing			X			X	
Drug/Placebo accountability						X	X
AUA Symptom score	X					X	X
BPH Impact Scale	X					X	X
Bladder Function	X					X	X
Erectile Function	X					X	X

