Ejaculatory Function	X					X	X
Adverse Events			X	X	X	X	X
Concomitant Meds	X	X	X	X	X	X	X

C Procedures

1 Visit 1: Screening

- Informed consent will be obtained prior to any research-related procedures.
- A physical including a digital rectal exam (DRE) will be performed.
- The subject's medical history and concomitant medications will be discussed and documented.
- The subject's vital signs will be taken and documented.
- The subject will complete the following questionnaires:
 - The AUA symptom score
 - BPH Impact Scale

- Bladder Function
- Erectile Function
- Ejaculatory Function
- The subject will undergo uroflow testing and will provide a post-void residual urine measurement.
- Blood (about 10 ccs or 2 teaspoons) will be drawn for CBC with platelets and PSA testing.
- A urinalysis (dipstick) will be performed.
- Dispense a Bactrim DS (antibiotic) 160/800mg tablet orally twice a day [Cipro (generic is permissible) 500 mg twice a day] with instructions to take for 1 day prior to biopsy, day of biopsy, and for 1 day following biopsy (total of 3 days).
- Subjects will be instructed to stop taking alpha blocker medications 7 days prior to biopsy.

2 Visit 2: Biopsy

- The subject's concomitant medications will be discussed and documented.
- The subject's vital signs will be taken and documented.
- A urinalysis (dipstick) will be performed to ensure that no infection is noted or suspected.
- Dispense an antibiotic
- Prostate size is measured via transrectal ultrasound on patients after receiving a Fleet's enema the morning of the examination.
- Transition zone biopsies will be performed.

3 Visit 3: Injection (4 weeks post-biopsy, ± 3 days)

- The subject's concomitant medications will be discussed and documented.
- The subject's vital signs will be taken and documented.
- Any adverse events experienced by the subject will be documented.
- **Injection Procedures:** onaBoNT-A solution does not contain a preservative, it should be administered within 4 hours after reconstitution and within 30 minutes of drawing into the syringe. The drug should be stored in a refrigerator when not in use during this period.
 - **Patient Preparation**
 - a. Patient is examined and submits urine for urinalysis which is examined by standard dipstick analysis or microscopic examination prior to randomization and preparing onaBoNT-A solution to ensure that no infection is noted or suspected.

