 - b. Prostate size is measured via transrectal ultrasound on patients after receiving a Fleet's enema the morning of the examination. The patient is placed in the lateral decubitus position with knees tucked against the chest and the transrectal probe introduced. A multi-planar probe that gives a 112° sector image is used to allow viewing in both transverse and longitudinal planes without moving the probe. The prostate size is measured initially using the height (H), width (W), and length (L) functions available on the ultrasound machine. Scanning of the prostate is carried out in two planes at

right angles to each other. The height and width are identified on a transverse image and recorded. The length is identified and recorded in the perpendicular longitudinal plane. The volume is calculated as a machine function using the formula $H \times W \times L \times \pi/6$ and recorded on hard copy.

- OnabotulinumtoxinA or Saline placebo Injection
 - a. Anesthesia is delivered according to the clinical practice of the center PI. Transrectal periprostatic block may be used with a 5 ml bolus of 1% lidocaine given just superolateral to each seminal vesicle as visualized using the transrectal sound probe in the sagittal plane. The bolus is given via an appropriately long 22-gauge needle.
 - b. The onabotulinumtoxinA toxin type A solution is given via the same approach using a second needle.
 - i. For men randomized to the 200 unit onaBoNT-A arm, 50 units per 1.0 ml volume is given at the following points of the transitional zone: left and right inferior and superior transitional zone.
 - ii. For men randomized to the placebo arm, 1.0ml of saline is given at the following points of the transitional zone: left and right inferior and superior transitional zone.
 - c. The needle is passed from posterior to anterior through the peripheral zone (PZ) into the base of the prostate at the transition zone/central zone junction on the left side. The needle is advanced to superior aspect of the transition zone.
 - d. Prior to injection of onabotulinumtoxinA the needle is aspirated to insure that there is no blood return. This is repeated prior to each injection.
 - e. The initial 1.0 ml of solution is first deposited at the superior (bladder base) transition zone (TZ). The needle is withdrawn to the inferior (apex) transition zone/central zone junction and the second 1.0 ml of solution is deposited on the same side as the needle is withdrawn.

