- The subject's vital signs will be taken and documented.
- The subjects returned drug product packaging will be reviewed and discussed with him.
- The subject will complete the following questionnaires:
- The AUA symptom score
- BPH Impact Scale
- Bladder Function
- Erectile Function
- Ejaculatory Function
- The subject will undergo uroflow testing and will provide a post-void residual urine measurement.

- Blood (about 5 ccs or 1 teaspoon) will be drawn for PSA testing.
- A urinalysis (dipstick) will be performed.
- Transition zone biopsies will be performed and the prostate volume will be measured.

IX BIOLOGICAL SPECIMENS

- A Prostate tissue will be collected at the time biopsy to conduct gene array studies to determine the effects of onaBoNT-A and tamsulosin on the genetic profile of human normal and BPH tissues. The specimens will be coded and will not include any subject identifying information. Testing on the tissue specimens will be conducted in [name] laboratory. The specimens will be stored until the end of the study at which time any unused specimens will be destroyed. These specimens will not be released to anyone not listed as an investigator on the protocol, nor will they be sold or transferred to any third party. If at any time the subject withdraws from this study, he will not be able to get the specimens back. Upon written request to [name], the stored samples will be destroyed but the data collected up until that time will not be deleted.

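### Baseline prostate volume is undefined although two pre-treatment scans are taken, and the order of scan and biopsy at Visit 7 is not fixed

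*Combined protocol and SAP*

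**What the plan says.** Prostate volume is measured at three points in the visit text of Section VIII.C.

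- **Visit 2 (biopsy).** "Prostate size is measured via transrectal ultrasound on patients after receiving a Fleet's enema the morning of the examination". The transition zone biopsies are the next bullet, so the scan is listed first.
- **Visit 3 (injection, about four weeks later).** Patient Preparation, item b, repeats the scan before the injection: "The prostate size is measured initially using the height (H), width (W), and length (L) functions available on the ultrasound machine". It gives the volume formula (H × W × L × π/6) and has the result calculated "and recorded on hard copy". This is the only full description of the method in the protocol.
- **Visit 7 (three months).** "Transition zone biopsies will be performed and the prostate volume will be measured".

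The schedule in Section VIII.B marks prostate volume at Visits 2 and 7 and leaves Visit 3 blank. Its enema row is marked at Visits 2 and 3 but not at Visit 7.

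Section X lists prostate volume among the secondary endpoints. Changes in these are to be compared between arms by an independent t-test or a Wilcoxon rank-sum test. No sentence says which pre-treatment volume is subtracted, or what is done with the other one.

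**The concern.** Two recorded pre-treatment values and no rule leave the definition of the endpoint open. A change from Visit 2, a change from Visit 3 and a change from their mean would each fit Section X, and they will give different estimates and p-values. Nothing stops the choice from being made after the results are known.

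There is also a missed opportunity. Ultrasound volume carries measurement error. The text already calls for a second scan, and using it in the analysis would tighten the between-arm comparison at almost no cost.

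The follow-up scan has a separate gap. At Visit 2 the scan is listed ahead of the cores. At Visit 7 one sentence names both tasks, biopsies first, without an order in time. If some or all final scans were made on a freshly biopsied gland, the first and last scans would not be taken under like conditions.

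The endpoint deserves this care. The background section says that the two randomised studies of the injection disagree on whether the prostate shrinks, and offers this trial as further evidence. Its table of earlier studies reports volume decreases from 0% to 68%, so readers will look at the within-arm change as well as at the comparison.

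**Working it through.** **1. The plan's own figure.** Nothing is sized on volume. Section XI sizes the AUA symptom score: difference 5.6, SD 6.3, two-sided 0.05, 90% power, 29 per group. An exact noncentral-t calculation gives power 0.904 at 28 and 0.914 at 29, so 29 is adequate. For 20% dropout, 29/0.80 = 36.25, rounded up to 37 per group and 74 in all. Volume does not enter, so these figures stand.

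**2. Second scan, change score.** Let E be the SD of measurement error on one scan and T the SD of true change. Assume independent errors and the same expected volume at both pre-treatment scans.

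- One baseline: variance = T² + 2E²
- Mean of two baselines: variance = T² + 1.5E²

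The documents give neither SD. I assume 3 to 8 cc for each.

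| E (cc) | T (cc) | One baseline | Mean of two | Fall in variance | Fall in SE |
|---|---|---|---|---|---|
| 3 | 8 | 82 | 77.5 | 5.5% | 3% |
| 5 | 5 | 75 | 62.5 | 17% | 9% |
| 8 | 3 | 137 | 105 | 23% | 12% |

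When E = T, 75/62.5 = 1.20, the same gain as 20% more men. The ceiling, with T = 0, is 1 − 1.5/2 = 25%.

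**3. Second scan, ANCOVA on log volume.** Let S be the SD of true log volume at baseline, and k the number of baseline scans.

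Residual variance = (S² + T² + E²) − S⁴/(S² + E²/k)

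I assume S = 0.4, E from 0.08 to 0.16 and T from 0.08 to 0.12.

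- E = 0.08, T = 0.12: 0.02695 with one scan, 0.02394 with two, a fall of 11%.
- E = 0.16, T = 0.08: 0.05407 with one scan, 0.04385 with two, a fall of 19%.

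These are gains over ANCOVA on one scan. Entering the two scans as separate covariates gives the same result as their mean when their errors are alike. It costs one more degree of freedom: with 58 completers, 58 − 4 = 54 instead of 58 − 3 = 55.

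**4. Visit 7 order.** Suppose every final scan followed the cores and the gland read larger by a common proportion s (assumed). Take a 49.7 cc gland (Section II) and, for illustration, 17% true shrinkage in the injected arm only (one open-label 200 U series in the background table). Changes are in cc.

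| s | Injected arm | Tamsulosin arm | Difference |
|---|---|---|---|
| 0 | −8.45 | 0.00 | −8.45 |
| 5% | −6.39 | +2.48 | −8.87 |
| 10% | −4.32 | +4.97 | −9.29 |
| 15% | −2.26 | +7.45 | −9.72 |

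The difference is −0.17 × 49.7 × (1 + s). With no true effect in either arm it stays at 0. The within-arm changes move by about 2.1 to 7.5 cc.

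**The case against.** The strongest reply is that the schedule settles the matter: volume is marked at Visits 2 and 7, so change naturally runs between them. The Visit 3 scan sits under patient preparation for the injection and may serve only that procedure. Both scans precede treatment, so either baseline gives an unbiased comparison of blinded arms. This is a fair reading, and it limits the harm. It is still an inference: Section X does not state it, and the Visit 3 text has the volume calculated and recorded.

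Three stronger conclusions are tempting, and the documents do not support them.

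- A reader might infer that the plan throws the Visit 3 value away. It does not; it is silent.
- A reader might infer that the Visit 7 scan is to be made on a freshly cored gland. The sentence joins two tasks and sets no sequence, and the bullet lists are nowhere said to be chronological. The schedule lists biopsy above volume for Visit 2 as well, where the text has the reverse. The blank enema cell at Visit 7 is firmer evidence that scan conditions may differ, but the anesthesia row is blank there too, so the Visit 7 entries may simply be abbreviated.
- A reader might infer that a post-core scan would spoil the treatment comparison. Step 4 shows that a common shift largely cancels between arms.

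The precision figures can also be challenged: every SD is assumed, and ANCOVA is not the planned test. That stands, and it is why ranges are given. Averaging the two baselines has a further weakness. Visit 3 falls about four weeks after biopsy, and any remaining swelling would raise the mean and exaggerate within-arm shrinkage.

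**Conclusion.** The point holds as an undefined baseline and an unfixed scan order for one secondary endpoint. The Visit 3 volume is recorded but unscheduled, and Section X does not say how it is used. The order at Visit 7 is open, so first and last scans may differ in condition; the within-arm change is what would suffer.

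The benefit of using both pre-treatment scans is about 5 to 23% of change-score variance, or about 11 to 19% of residual variance under log-scale ANCOVA. Both ranges rest on assumed SDs and on independent measurement errors. The 5 to 15% swelling in step 4 is likewise only an illustration. The between-arm test stays valid whichever pre-treatment scan is used, provided the choice is fixed in advance. The primary symptom-score analysis and the 29, 37 and 74 figures are not affected.

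**What to change.** 1. Reconcile the schedule in Section VIII.B with the Visit 3 text by marking prostate volume at Visit 3, and collect that value on the case report form.
2. In Section X, pre-specify that the between-arm volume analysis is an ANCOVA with the Visit 2 and Visit 3 volumes both entered as covariates, and fix the scale (log volume is a natural choice). With separate covariates, a common post-biopsy shift at Visit 3 goes into the intercept and does not bias the comparison.
3. Name the Visit 2 volume, the pre-biopsy scan, as the baseline for within-arm change.
4. State at Visit 7 that volume is measured before the cores, by the same method as at Visit 2, and reconcile the text with the schedule on how the man is prepared for that scan.

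The text already calls for both pre-treatment scans, so the cost is a few sentences, one extra data field and a model beyond the planned t-test or Wilcoxon test. It should be settled before unblinding.

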We identified that the epithelial cells gene profile indicated an expected acute phase response, driven most likely by serum response factor, as this seems to be the most common motif that regulates this set of genes (SRF:Serum response factor (c-fos serum response element-binding transcription factor)). Endothelin* and endothelin receptors types A and B were among the most upregulated genes. Insulin I* and II* and insulin-like growth factor 1 and insulin-like growth factor binding protein 4 were also significantly upregulated. Numerous other growth factors were also upregulated including c-fos induced growth factor, connective tissue growth factor as well as epidermal growth factor receptor. Fas ligand (TNF superfamily, member 6) and tumor necrosis factor receptor superfamily, member 1b were also upregulated.

The epithelial cells acquired a more mesenchymal phenotype with production of multiple collagens (collagen, type XVI, alpha 1, collagen, type XIV, alpha 1, collagen, type III, alpha 1, collagen, type I, alpha 1), probably responsible for the collagenous nodules. Genes usually identified with stemness properties were also upregulated (noggin, secreted frizzled-related protein 4, wingless-related MMTV integration site 11, dickkopf homolog 4).

Denervation effects on Non-Neoplastic Human Prostate Epithelium: As an initial clinical translation and proof-of-concept study, we next evaluated tissues from three patients with prostate cancer enrolled in a Phase I clinical trial examining the effects of onaBoNT-A injections on prostate epithelial biology. Patients received unilateral injection with onaBoNT-A (100 units in 1.0 ml) into one transition lobe and a vehicle control injection (i.e. saline) into the contralateral lobe. Examination of tissue from radical prostatectomies performed 4 weeks after injection

revealed a significant or trend increase in the apoptotic ratio by TUNEL studies in two out of three patients (Figure 5). No significant changes were observed in the proliferation index, measured by Ki-67.

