 - f. The needle is passed from posterior to anterior through the peripheral zone (PZ) on the right side into the base of the prostate at the transition zone/central zone junction on the left side. The needle is advanced to superior (bladder base) aspect of the transition zone.
 - g. The 1.0 ml of solution is first deposited at the inferior (apex) transition zone (TZ). The needle is withdrawn to the inferior (apex) transition zone/central zone junction and the second 1.0 ml of solution is deposited on the same side as the needle is withdrawn.
 - h. The needle, syringe, and vial are disposed of in a biohazard container according to institutional policy, and a witness signs a form.
 - i. After the injection, the patient remains in the clinic until a spontaneous void has occurred.
- Subjects will receive an adequate supply of tamsulosin/placebo with instructions on dosing.

- Because of the theoretical possibility of diffusion of onabotulinumtoxinA into seminal fluid, and no evidence to the contrary, those patients who engage in sexual intercourse are required to use condoms for 48 hours after the injection.

4 Visits 4 (Day 3 post-injection)

The subjects will be contacted by telephone 3 days after injection to monitor for symptoms of infection or bleeding.

5 Visits 5 (1 Week \pm 3 days post-injection)

The subjects will be contacted by telephone 1 week after injection to collect medical events, concomitant medication update, and status.

6 Visit 6: (4 Weeks post-injection \pm 3 days)

- The subject's concomitant medications will be discussed and documented.
- The subject's vital signs will be taken and documented.
- Any adverse events experienced by the subject will be documented.
- The subject will undergo uroflow testing and will provide a post-void residual urine measurement.
- A urinalysis (dipstick) will be performed.
- The subjects returned drug product packaging will be reviewed and discussed with him. A new supply of tamsulosin will be dispensed.
- The subject will complete the following questionnaires:
- The AUA symptom score
- BPH Impact Scale
- Bladder Function
- Erectile Function
- Ejaculatory Function
- Dispense an antibiotic

7 Visit 7: End of Study (3 months post-injections \pm 3 days)

- A physical including a digital rectal exam (DRE) will be performed.
- The subject's concomitant medications will be discussed and documented.
- Any adverse events experienced by the subject will be documented.

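### Injection steps f and g contradict the four-site rule in step b, so no written step delivers to the right superior transition zone

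*Combined protocol and SAP*

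**What the plan says.** Section V.A (Drug Information) sets the total at 200 U in 4 cc of saline, or 4 cc of saline alone for placebo. Section VIII.C.3 (Visit 3: Injection) divides this in step b. In each arm, 1.0 ml goes to each of the points "left and right inferior and superior transitional zone", at 50 U per ml in the toxin arm.

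Steps c to e describe the left-sided pass. The needle goes to the left junction and is advanced to the superior transition zone. Then "The initial 1.0 ml of solution is first deposited at the superior (bladder base) transition zone (TZ"), after which the needle is withdrawn to the apex for the second 1.0 ml.

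Steps f and g describe the second pass:

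- Step f passes the needle through the peripheral zone "on the right side into the base of the prostate at the transition zone/central zone junction on the left side". It continues: "The needle is advanced to superior (bladder base) aspect of the transition zone".
- Step g opens: "The 1.0 ml of solution is first deposited at the inferior (apex) transition zone (TZ"). It continues: "The needle is withdrawn to the inferior (apex) transition zone/central zone junction", where the second 1.0 ml is given.

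For tissue sampling, section VIII (Design) specifies six cores per volunteer, described as "3 cores from the left and right transition zone". The human pilot in section II put toxin into one transition lobe and "a vehicle control injection (i.e. saline) into the contralateral lobe".

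**The concern.** Steps f and g should mirror steps c to e on the right, and they fail to do so in two places. Step f names the wrong side as the target. Step g names the apex for both deposits. The two steps also disagree with each other: step f has just taken the needle to the bladder base, so the next deposit cannot be at the apex, and a needle already at the apex cannot be withdrawn to it.

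The same text governs the toxin and the saline injections. An operator who follows the steps as written departs from step b.

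What is at stake is mainly the tissue objective, which concerns pathology and RNA profiles in transition zone biopsies. On the fully literal reading, the right-sided post-treatment cores come from a side where no deposit was planned. The pilot used the uninjected side as its control, so the team itself treats side of injection as relevant to tissue findings.

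**Working it through.** **Inputs.** Total 200 U in 4 cc (section V.A); 50 U per 1.0 ml at four points (section VIII.C.3, step b); side and level of each deposit (steps c to g).

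**The plan's own figure.** 4 sites × 50 U = 200 U, and 4 × 1.0 ml = 4.0 ml. Step b therefore agrees exactly with section V.A.

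**Deposits mapped to sites.** Steps c to e give 50 U at left superior and 50 U at left inferior. Steps f and g place the remaining 2 × 50 = 100 U, and where it goes depends on the reading.

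| Reading | L sup | L inf | R sup | R inf | Total | Left / right |
|---|---|---|---|---|---|---|
| Step b (planned) | 50 | 50 | 50 | 50 | 200 U | 100 / 100 |
| f read as right, g literal | 50 | 50 | 0 | 50 + 50 = 100 | 200 U | 100 / 100 |
| f and g both literal | 50 | 50 + 50 + 50 = 150 | 0 | 0 | 200 U | 200 / 0 |

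In volume, the three rows are 1/1/1/1, 1/1/0/2 and 1/3/0/0 ml.

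**Displaced dose.** This is half the sum of absolute differences from plan:

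- f read as right, g literal: (0 + 0 + 50 + 50)/2 = 50 U, and 50/200 = 25%.
- Both literal: (0 + 100 + 50 + 50)/2 = 100 U, and 100/200 = 50%.

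**Cores.** Reading the biopsy sentence as three cores from each side, 3/6 = 50% of post-treatment cores would come from a side without a planned deposit. This applies to the fully literal reading only. In the other reading each side still receives 100 U.

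**Evidence of intent.** Step f enters on the right and goes to the bladder base; step g then withdraws to the apex. That movement fits only a superior-then-inferior sequence on the right, matching step e.

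**After correction.** With a right-sided target in step f and a superior first deposit in step g, the allocation is 50/50/50/50 U, or 200 U in 4.0 ml, in agreement with step b and section V.A.

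**The case against.** The strongest reply accepts the contradiction and disputes its weight.

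- **Intent is recoverable.** Step b states the four-site rule once for each arm, and an experienced operator would probably inject correctly. This stands, and it is why the point is a correction to make and not a flaw in the design.
- **The fully literal reading is barely workable.** It needs a right-sided entry to cross to a side that already has both deposits, followed by a withdrawal from apex to apex. Step g names no side for its first deposit, and its same-side wording for the second could mean the right. This too has force. The 50/150/0/0 U row is best taken as the outer bound of what the text permits. The 50/50/0/100 U row is the milder case.
- **The tissue argument is limited.** Visit 2 biopsies precede injection, so only post-treatment cores could be affected. Section IX.A compares arms and time points, not sides, and it counts apoptosis and proliferation in the highest-staining areas, which may reduce dependence on core position. The pilot does not show that a change of level within a lobe matters. All of this stands and narrows the consequence.
- **No inferential effect is shown.** Total dose, sample size and planned analysis are unchanged, and the same wording applies to toxin and saline, so it does not by itself threaten blinding. This is agreed.

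None of this removes the conflict. Step b says where the deposits belong, but the step-by-step text still sends the operator elsewhere, and nothing in the protocol rewords steps f or g.

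**Conclusion.** The concern holds. Steps f and g are wrong as written and contradict step b; under either reading the right superior site receives 0 U where 50 U is planned. The displaced share is 25% of the dose if only step g is followed literally and 50% if both steps are. Total dose and volume are unaffected.

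These figures describe the text. They do not estimate what operators did. The 3-of-6-core consequence rests on the fully literal reading and applies only after treatment. No effect on the AUA symptom score comparison, power, safety or operator variability is asserted. This is an internal inconsistency, very likely a copying slip, in instructions that govern delivery of the study product, and it should be corrected.

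**What to change.** Make two edits in section VIII.C.3, both to be confirmed by the clinical team:

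1. Step f: change the side of the target junction from left to right.
2. Step g: change the level of the first deposit from inferior (apex) to superior (bladder base).

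The cost is a few words in two steps, with no added procedure, visit or patient. Recording the side and level of each deposit on the case report form would let departures be seen later. It is optional, and the correction does not depend on it.

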Mean AUA score reduction in the alpha blocker group is expected to be at most 9.6 with a standard deviation of 6.3 based on published results of a randomized trial comparing tamsulosin versus placebo.²⁹ However, that same study showed a strong pill placebo effect with a mean reduction of 5.5, resulting in a treated reduction of 4.1 above the placebo group. Another study¹³, comparing botulinum toxin to placebo, showed a mean score reduction in the botulinum group of 15.2 and no placebo change. For our study, we will assume a mean reduction of 15.2 in the onaBoNT-A group which is 9.7 more than the pill placebo effect, a mean reduction of 9.6 in the alpha blocker group and a standard deviation of 6.3 for both groups. Based on these assumptions, a sample size of 29 subjects per group will achieve 90% power to detect a difference of 5.6 with an alpha level of 0.05 using the 2-sided independent t-test. Sample size calculations were done using PASS 2008 software (Hintze, J. (2008). NCSS, LLC. Kaysville, Utah. www.ncss.com).

The drop-out rate in the alpha-blocker study was as large as 20% and our own experience with onabotulinumtoxinA (onaBoNT-A) in the MIST-2 trial has demonstrated a dropout rate of 14%. So adjusting our sample size for an expected dropout rate of 20%, we will enroll 37 patients into the onaBoNT-A and tamsulosin groups for a total of 74 patients. To address some of the problems with possible attrition bias, we will use intent to treat analysis and patients will be kept in the study as long as possible even if they are no longer on treatment. We will also compare results between the intent to treat groups and the subjects who completed treatment to determine if differences exist.

XII. RETENTION AND DROPOUT/WITHDRAWAL

Minimal dropout or loss to follow-up is expected in this cohort, especially given the short follow-up. However, if a patient drops out before 4 weeks, he will be replaced so that the required sample size is realized. For purposes of tracking the feasibility of conducting a trial of treatment with onaBoNT-A, reasons for dropout or withdrawal will be documented.

XIII. CRITERIA FOR DISCONTINUING THE STUDY

- A Subjects unable to tolerate [tamsulosin or] onaBoNT-A due to side effects.
- B Subjects can request removal from the study for any reason at any time.
- C Subjects may be withdrawn at any time at the discretion of the investigator for safety, compliance, or other reasons.

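### No visit, call or adverse-event window follows the second prostate biopsy, which is done at the end-of-study visit

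*Combined protocol and SAP*

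**What the plan says.** Section VIII (Design) sets the biopsy times: "Transition zone biopsies will be performed at Visit 2, 30 days before treatment, and again at 3 months post-treatment". Section IX.A gives the purpose: "Prostate tissue will be collected at the time biopsy to conduct gene array studies".

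The second biopsy belongs to section VIII.C.7, headed "Visit 7: End of Study" and placed 3 months after injection, give or take 3 days. The visit's final bullet is "Transition zone biopsies will be performed and the prostate volume will be measured". Its adverse-event bullet, "Any adverse events experienced by the subject will be documented", comes earlier in the same list. In the schedule of events (VIII.B), Visit 7 is the last column and the adverse-event row is marked for Visits 3 to 7.

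Follow-up of the other procedures is as follows:

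- **First biopsy (Visit 2).** Visit 3, about 4 weeks later, carries the same adverse-event bullet (VIII.C.3).
- **Injection (Visit 3).** Men are "contacted by telephone 3 days after injection to monitor for symptoms of infection or bleeding" (VIII.C.4) and then "contacted by telephone 1 week after injection to collect medical events, concomitant medication update, and status" (VIII.C.5). Adverse events are also documented at week 4 and at 3 months.

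Section XV (Risks and Discomforts, entries A to I) covers the ultrasound examination but has no entry for the biopsy. Section XX (Adverse Event Reporting) points to FDA, ICH and IRB rules and sets no collection period.

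**The concern.** Infection, bleeding and urinary retention after prostate needle procedures need not show themselves on the day. The protocol accepts this for the injection, since the day-3 call asks specifically about infection and bleeding. The second biopsy gets no such contact because study participation ends at the visit where it is done.

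Two things are at stake. One is the safety of participants: the trial would not actively detect a delayed complication of a procedure done to obtain research tissue. The other is completeness: safety data after the last biopsy would cover the same day only. Both arms are affected alike, and no bias in the treatment comparison is alleged.

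**Working it through.** **Step 1. Set the three procedures side by side (VIII.B and VIII.C).**

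| Procedure | Visit | Scheduled adverse-event collection afterwards |
|---|---|---|
| First biopsy | 2 | Visit 3, at 28 ± 3 = 25 to 31 days |
| Injection | 3 | Day 3 call; week-1 call at 7 ± 3 = days 4 to 10; week 4 visit; 3-month visit |
| Second biopsy | 7 | None after the day itself |

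The number of later collection points is 1, 4 and 0. Visit 3 is not a dedicated post-biopsy contact, but it does collect events arising since the first biopsy.

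**Step 2. Look for anything else that closes the gap.** The schedule marks antibiotic dispensing at Visit 6, and an antibiotic and a dipstick urinalysis at Visit 7. These help prevent infection or screen for it on the day; they do not collect later events. Sections XV and XX, as described above, give no post-biopsy window either.

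**Step 3. Reproduce the enrolment figure (XI).** 29 per group / (1 − 0.20) = 36.25, rounded up to 37; 2 × 37 = 74. This agrees with the protocol.

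**Step 4. Count the men affected.** The dropout rates come from section XI: 20% as planned, and 14% from the earlier onaBoNT-A trial that it cites.

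- 20% dropout: 74 × 0.80 = 59.2, about 59
- 14% dropout: 74 × 0.86 = 63.6, about 64
- no dropout: 74

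**Step 5. Express this as a share of all biopsies**, that is, second biopsies / (first + second). It is assumed that 74 men have the first biopsy and that every man reaching Visit 7 has the second.

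- 59 / (74 + 59) = 59/133 = 44%
- 64 / (74 + 64) = 64/138 = 46%
- 74 / (74 + 74) = 74/148 = 50%

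**Step 6. Allow for replacement.** Section XII says that "if a patient drops out before 4 weeks, he will be replaced so that the required sample size is realized". As a limiting case, suppose all of the 20% leave in that window, after a first biopsy: 74 × 0.20 = 14.8, about 15 men. If all 15 are replaced and 74 finish, first biopsies number 74 + 15 = 89, and the share is 74 / (89 + 74) = 74/163 = 45%. The share hardly moves.

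**Step 7. Missed events.** The documents give no complication rate for biopsy, so none is calculated.

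**The case against.** The best opposing case accepts the reading of the schedule and argues that the gap is minor.

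- **Dedicated calls are reserved for the study product.** Neither biopsy has its own call, and Visit 3 exists to give the injection. This is correct, and it means the plan does not contradict itself. Still, the first biopsy has a later collection point in practice and the second has none.
- **Routine care would pick events up.** Section XVIII describes everything other than the study products and anesthesia as standard of care, and the men are patients at the same centre. That statement is in the section on costs to subjects, while IX.A gives gene array work as the reason for taking the tissue. Usual care or spontaneous reports may catch some events, but nothing in the protocol tells staff to look for or record them after Visit 7.
- **Some text could not be seen.** The consent pages were removed for this review, and the QA/QC protocol in Appendix B is listed without its content. Either could hold a call-back instruction. This limits the claim to the visible protocol, but the visible schedule is what defines adverse-event collection.
- **The needle route is not stated.** The biopsies are described only as guided by transrectal ultrasound. The enema and antibiotic make a transrectal route likely, but that is an inference. The gap does not depend on it.
- **The percentages say little.** This has force: a share near one half follows almost automatically from two biopsies per man. The replacement case is a limit, not a forecast. Men biopsied but never randomized would raise the number of first biopsies above 74. The count of men is the more useful figure.
- **No planned analysis is affected.** True. Section X specifies no safety analysis, and the primary comparison is untouched.

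**Conclusion.** The concern holds. As the schedule is written, every man who has the second biopsy leaves the study that day, and delayed infection, bleeding or retention has no scheduled collection point. That is about 59 to 74 men, or about 44% to 50% of all biopsies.

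These figures rest on 74 men enrolled, dropout between 0% and 20%, and a second biopsy in every man who reaches Visit 7. The conclusion itself needs none of them, since it follows from the order of events in the schedule. It applies to the protocol as seen, without the consent pages or the content of Appendix B. The change should be made: it closes a safety gap cheaply, although the trial's efficacy conclusions do not depend on it.

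**What to change.** Add one telephone contact about 1 week after the Visit 7 biopsy, asking about infection, bleeding and retention. A further call at day 3, mirroring the follow-up of the injection, is optional. Add the contact to VIII.B and VIII.C, extend the adverse-event row to it, state in section XX that collection runs to that contact, and define it as the end of study in place of Visit 7.

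The cost is about 59 to 74 short calls in total, one per man, and about one more week of participation for each. No extra clinic visit, procedure or assessor is needed, and the primary endpoint and its analysis stay as they are.
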